## **4.2. Number of Clinical Study Sites**

Approximately █ clinical trial centres are expected to participate in this study. Additional sites may be used in order to supplement recruitment.

## **4.3. Number of Participants**

Up to 27 participants will be assigned to receive the study intervention in order to achieve 18 evaluable participants for this study. Additional information is provided in [Section 13.1](#).

## **4.4. End of Study Definition**

A participant is considered to have completed the study if they have completed all phases of the study, including the last scheduled procedure shown in the SoA ([APPENDIX 1](#)).

The end of the study is defined as the date of the last visit of the last participant in the study or last contact, whichever occurs last.

## 5. STUDY INTERVENTION

Please refer to the separate pharmacy manual for more detailed information about the study intervention.

The study intervention, GWP42003-P oral solution, contains 100 mg/mL CBD dissolved in the excipients sesame oil and anhydrous ethanol (10% v/v), with sweetener (sucralose), and strawberry flavouring (Table 1).

Table 1 Formulation of GWP42003-P Oral Solution	
Ingredients	Quantity
CBD	100 mg/mL
Anhydrous ethanol	79 mg/mL
Sucralose	0.5 mg/mL
Strawberry flavour	0.2 mg/mL
Refined sesame oil	make up to 1 mL

Abbreviations: CBD = cannabidiol.

## 5.1. Packaging, Storage and Drug Accountability

### 5.1.1. Packaging and Labelling

The study intervention will be manufactured, packaged, labelled, and/or distributed by the sponsor or delegated contractors. The study intervention will be presented in 105 mL amber glass bottles containing 100 mL of 100 mg/mL CBD solution with child resistant screw caps and packed in cartons. Sufficient study intervention will be dispensed at each relevant visit considering the dose group and the weight of the participant. A unique identification number will be used to identify each box and the study intervention it contains. The unique identification number together with the packaging lot number (PLN) will permit full traceability of manufacture, pack and label activities conducted at or on behalf of sponsor and the study intervention information held on the RTSM system. The sponsor will ensure that all study intervention provided is fully labelled and packaged. Label text will include the following information, as a minimum:

- Sponsor's name and address.
- Product identification (e.g., GWP42003-P or CBD-OS).
- Dose and/or potency (e.g., "100 mg/mL GWP42003-P").
- Study code number.
- Expiry date.
- Storage conditions.
- Instruction: "For clinical trial use only".
- Instruction: "Keep out of the sight and reach of children".
- Any other information required by local regulatory authorities.

Directions for use will be provided separately to the participant.

#### **5.1.2. Storage**

The study intervention must be stored upright at room temperature (< 30°C) and must not be refrigerated or frozen. It must also be kept away from heat and direct sunlight.

The study intervention must be stored in compliance with the local regulations for a controlled drug (if applicable to the country). The sponsor must approve the storage location and facilities. Temperature records of the clinical site storage location must be maintained (recording a minimum of Monday through Friday, excluding public holidays) from date of receipt of first shipment until end of study dispensing period at each site. These records must contain at least the minimum and maximum daily temperatures and must be made available to the appropriate sponsor personnel for review throughout the study. Temperature during transit of GWP42003-P to the site must be checked on receipt and compliance/noncompliance to the minimum and maximum recorded.

Should storage conditions deviate from these specified requirements, the sponsor study monitor must be contacted immediately to confirm if the study intervention remains suitable for use. The study intervention must be placed under quarantine until written confirmation is received that the study intervention is suitable for use.

Caregivers will be provided with instructions regarding home storage requirements for the study intervention.

#### **5.1.3. Supply and Return of Study Intervention**

At study initiation and as needed thereafter, the study intervention will be shipped to the identified responsible person, such as the pharmacist, at the investigator's site, who will check the amount received (against the RTSM Shipment Request) and condition of the drug (i.e., integrity, physical appearance, temperature during transit). Details of the study intervention received will be recorded in the study intervention accountability record (see [Section 5.1.4](#)). The site will acknowledge the study intervention receipt via the RTSM and will complete any receipt forms required. Study intervention will be dispensed and returned as detailed in [Section 8.5](#). As directed, all supplies, including unused, partially used, or empty containers, will be returned to the sponsor or destroyed at a sponsor-approved site if agreed in writing by the study monitor.

#### **5.1.4. Study Intervention Accountability**

The investigator has overall responsibility for the accountability of all used and unused study intervention. A drug accountability record for the study intervention must be kept current and must contain:

- Study code.
- Pack number, PLN, date of receipt, and quantity of study intervention received.
- Participant's study identification and/or treatment number.
- Date and quantity of study intervention dispensed.
- The initials of the dispensing/dosing party.

- Date and quantity of study intervention returned to the investigator.
- Study intervention expiry dates.

Refer to [APPENDIX 1](#) for when the study intervention will be dispensed. Participants' caregivers will be asked to return all study intervention (unused, partially used, and empty containers) at each relevant visit. The site will check the returned study intervention against the usage recorded in the diary. Any discrepancies will be discussed with the caregiver at the time of the visit and documented accordingly within the participant's source documents.

The investigator must inform the sponsor promptly of all missing or unaccountable study intervention.

A record of returned study intervention must be completed and included in the shipment of used and unused study intervention to the relevant drug distribution depot. At the end of the study, a record/statement of reconciliation must be completed and provided to the sponsor.

These inventories must be made available for inspection by an authorised sponsor representative and local officials or regulatory agency inspectors.

Please refer to the separate pharmacy manual for more detailed information on the study intervention.

#### **5.1.5. Post-Study Provision**

Participants will not have access to GWP42003-P through an expanded access program after the study is completed; participants may have access to the commercial product upon completing the study as permitted per local health authorities.

A summary of the results of this study will be made available on <http://www.clinicaltrials.gov> and <https://euclinicaltrials.eu/>(as applicable), as required by US and EU law.

## 6. PARTICIPANT ELIGIBILITY

Investigators are responsible for confirming participant eligibility and will be required to maintain a log that includes limited information about all screened participants (e.g., initials, age, and sex [as allowed per local regulations]) and outcome of screening.

### 6.1. Inclusion Criteria

For inclusion in the study participants must fulfil ALL of the following criteria:

- 6.1.1 Participants with TSC (1 month to < 2 years of age), or DS (1 year to < 2 years of age), or LGS (1 year to < 2 years of age) within the specified age range at the time of initial informed consent.
- 6.1.2 Participants with TSC must have a diagnosis per the 2012 International Tuberous Sclerosis Complex Consensus Conference ([Northrup 2013](#))[\(APPENDIX 3\)](#). Participants with LGS or DS must have a diagnosis that is consistent with International League Against Epilepsy (ILAE) guidelines and confirmed by the Epilepsy Study Consortium (ESCI) (also refer to [Section 9.1.12.1](#)) ([Specchio 2022](#), [Zuberi 2022](#)).
- 6.1.3 Participants who have uncontrolled seizures, and who are currently receiving 1 or more ASMs.
- 6.1.4 Parent(s)/LAR is/are willing and able to give informed consent for participation in the study.
- 6.1.5 Parent(s)/LAR is/are willing and able (in the investigator's opinion) to comply with all study requirements (including accurate electronic patient-reported outcome [ePRO] diary completion).
- 6.1.6 Caregiver completes at least 75% of ePRO and paper seizure diary entries during the 28 days of the baseline period ( $\geq$  21 days of entries).
- 6.1.7 A suitable VEEG, as available in the medical records, within 1 year of Visit 1. When a historical VEEG is not available, and if clinically indicated and appropriate due to uncertainties or new seizures, a VEEG will be completed and read to confirm diagnosis prior to Visit 3. All VEEGs are to be read at baseline by the investigator and an independent reviewer.
  - A suitable VEEG meets all the following criteria:
    - i. Multichannel (minimum 8-channel)
    - ii. Prolonged continuous recording up to 24 hours
    - iii. Completed within 1 year of Visit 1
    - iv. Consistent with the participant's current seizures (in the investigator's opinion)
    - v. Can be reviewed by the investigator and an independent reviewer prior to Visit 3
    - vi. Consistent with a diagnosis of inadequately-controlled seizures
- 6.1.8 Currently taking  $\geq$  1 ASMs at a dose that remains stable 2 weeks prior to Visit 3 and during the treatment period. Where required for participant safety, adjustments of concomitant ASMs or addition of new ASM may be permitted following discussion with the medical monitor.
  - Adrenocorticotropic hormone (ACTH) or high dose corticosteroids for the treatment of IS/ES are counted as ASMs.

- 6.1.9 Has seizures that are not adequately controlled through their current ASMs, defined as  $\geq 1$  seizure reported on the seizure diary during the screening/baseline period.
- 6.1.10 Parent(s)/LAR is/are willing to allow the responsible authorities to be notified of participation in the study, if mandated by local law.
- 6.1.11 Parent(s)/LAR is/are willing to allow the participant's primary care practitioner (if they have one) and consultant (if they have one) to be notified of participation in the study if the primary care practitioner/consultant is different from the investigator.

## 6.2. Exclusion Criteria

The participant may not enter the study if ANY of the following apply:

- 6.2.1 Has clinically significant unstable medical condition other than epilepsy.
- 6.2.2 Has had clinically significant symptoms or a clinically significant illness within the 4 weeks prior to Visit 1, other than epilepsy, which in the opinion of the investigator could affect seizure frequency.
- 6.2.3 Has undergone general anaesthesia within 4 weeks prior to Visit 1.
- 6.2.4 Has undergone surgery for epilepsy within 6 months prior to Visit 1 or has plans to undergo surgery for epilepsy during the study.
- 6.2.5 Has taken felbamate  $< 1$  year prior to Visit 1.
- 6.2.6 Is  $< 1$  year of age and taking valproic acid.
- 6.2.7 Has tumour growth which, in the opinion of the investigator, could affect participant safety.
- 6.2.8 Has clinically significant abnormal laboratory values, in the investigator's opinion, at screening/baseline.
- 6.2.9 Has clinically significant abnormalities in the ECG measured at screening/baseline.
- 6.2.10 Has any concurrent cardiovascular conditions that will, in the investigator's opinion, interfere with the ability to assess their ECGs.
- 6.2.11 Has any known or suspected hypersensitivity to cannabinoids or any of the excipients of the study intervention such as sesame seed oil.
- 6.2.12 Has significantly impaired hepatic function prior to Visit 3, defined as:
  - Serum alanine aminotransferase (ALT) **or** aspartate aminotransferase (AST)  $> 3 \times$  upper limit of normal (ULN) **and** (total bilirubin [TBL]  $> 2 \times$  ULN **or** international normalised ratio [INR]  $> 1.5$ ).
  - Serum ALT or AST  $> 5 \times$  ULN.
  - Serum ALT or AST  $> 3 \times$  ULN with the presence of fatigue, nausea, vomiting, right upper quadrant pain or tenderness, fever, rash, and/or eosinophilia ( $> 5\%$ ).
  - Elevated ALT or AST should be discussed with the medical monitor prior to Visit 3; the medical monitor may allow for a confirmatory re-draw prior to Visit 3.
- 6.2.13 Has received another study intervention within 4 weeks prior to Visit 1 or plans to take another study intervention during the study.
- 6.2.14 Caregiver is currently giving or has given recreational or medicinal cannabis, cannabinoid-based medications (including Sativex) or CBD (including

Epidiolex/Epidyolex [GWP42003-P]) to the participant within the 4 weeks prior to Visit 1 **or** is unwilling to abstain from doing so for the duration of the study.

- 6.2.15 Mother (if breastfeeding) is currently using or has used recreational or medicinal cannabis, cannabinoid-based medications (including Sativex) or CBD (including Epidiolex/Epidyolex [GWP42003-P]) within the 4 weeks prior to Visit 1 **or** is unwilling to abstain from doing so for the duration of the study.
- 6.2.16 Has any other clinically significant disease or disorder which, in the opinion of the investigator, may either put the participant, other participants, or site staff at risk because of participation in the study, may influence the result of the study, or may affect the participant's ability to take part in the study.
- 6.2.17 Any clinically significant abnormalities identified following a physical examination of the participant that, in the opinion of the investigator, would jeopardize the safety of the participant if they took part in the study.
- 6.2.18 Has previously been enrolled into this study.
- 6.2.19 Has plans to travel outside their country of residence during the study, unless the participant has confirmation that the study intervention is permitted in the destination country and all stops along the way.

## **7. PARTICIPANT ENROLMENT**

Before participants may be entered into the study, the sponsor requires a copy of the relevant site's Institutional Review Board (IRB)/Independent Ethics Committee (IEC) written approval of the protocol, ICF, and other participant information material. Participants will be considered enrolled in the study from the time of the parent(s)/LAR providing written informed consent. The participant's parent(s)/LAR must personally sign and date the ICF regulations, prior to any procedures being performed (refer to [Section 9.1.1](#) and [Section 15.2](#)).

### **7.1. Enrolment Stratification**

Enrolment will be stratified via the RTSM to ensure that at least 5 participants each with LGS and DS (1 to  $< 2$  years of age) and 8 participants with TSC (4 participants  $< 1$  year of age and 4 participants aged 1 to  $< 2$  years) are included in this study in order to achieve 18 evaluable participants. All participants will receive open-label study intervention in this nonrandomised study.

## 8. TREATMENT PROCEDURES

### 8.1. Study Intervention Dosage, Administration and Schedule

For details regarding study intervention formulations, see [Section 5](#).

#### 8.1.1. Dose Administration

GWP42003-P will be administered as adjunctive therapy (i.e., in addition to the participant's current ASM regimen) orally b.i.d. (morning and evening) using the syringe(s) provided. In participants with G- or NG-tubes but where oral dosing of GWP42003-P is possible, oral dosing is preferable. Only in participants where oral dosing is not possible, and following consultation with the medical monitor, should GWP42003-P be administered via G- or NG-tubes made from silicon only (feeding tubes must be flushed with 15 to 30 mL of water before and after GWP42003-P dosing and also flushed after administration of concomitant medications to be taken before GWP42003-P [volume of water may be modified for participants with fluid restrictions]). Volume of GWP42003-P to be determined by participant's weight and assigned dose.

GWP42003-P should be taken at about the same time each day consistently with or without food. The time of GWP42003-P administration in relation to food should be kept consistent throughout the study.

Route of administration with GWP42003-P (oral or with G- or NG-tubes) should remain consistent throughout the study. Any changes in the route of administration should be captured in the participant's medical records.

#### 8.1.2. Dose Escalation and Dose Adjustments

The 52-week treatment period includes a fixed 2-week titration schedule followed by flexible dose optimisation. The optimal dose will be based on the participant's observed efficacy, safety, and tolerability per the investigator's clinical judgement.

On Day 1 (Visit 3) of treatment with GWP42003-P, participants will initiate the fixed 2-week titration of GWP42003-P, beginning with a dose of 5 mg/kg/day (2.5 mg/kg b.i.d.). On Day 8 ( $\pm$  3 days), the dose will be increased to the target dose level of 10 mg/kg/day (5 mg/kg b.i.d.). Participants will be observed on Day 15 (Visit 5).

After Day 15 (Visit 5), the GWP42003-P dose may be escalated further based on individual clinical response and tolerability using a flexible titration schedule, per the investigator's clinical judgement. If, in the investigator's opinion, the participant is experiencing a clinically meaningful improvement in seizures, investigators will have the option to maintain or increase a participant's dose at any time during or between scheduled visits until EOT. Doses may be increased up to a maximum of 20 mg/kg/day (10 mg/kg b.i.d.) for LGS and DS or 25 mg/kg/day (12.5 mg/kg b.i.d.) for TSC, in maximum weekly increments of 5 mg/kg/day ( $\leq$  2.5 mg/kg b.i.d.). If possible, changes in dose should be avoided during the 3 days prior to PK visits or before PK samples have been collected on the day of PK study visits (as specified in [APPENDIX 1](#)) unless clinically indicated for safety ([Section 9.1.10.1](#) provides additional details).

A titration schedule (including the fixed 2-week titration to the target dose and a suggested titration schedule up to the maximum dose) is provided in [Table 2](#). Per the table, a participant's dose may be escalated to up to 15 mg/kg/day ( $\leq 7.5$  mg/kg b.i.d.) on or after Days 15, up to 20 mg/kg/day ( $\leq 10$  mg/kg b.i.d.) on or after Day 22, and up to 25 mg/kg/day ( $\leq 12.5$  mg/kg b.i.d.; TSC only) on or after Day 29. However, the titration schedule starting at Day 15 in [Table 2](#) is optional; investigators should use their clinical judgement when titrating a participant's dose. Any adjustments to a participant's dose will require follow-up within 7 days via an in-clinic visit or telephone follow-up, as determined by the investigator, to evaluate participant safety. An unscheduled phone contact (documented as an unscheduled phone visit) or unscheduled clinic visit must be recorded in the eCRF.

Table 2 Dose Titration		
Days	Daily Dose	Morning and Evening Dose
Fixed titration to target dose		
1 to 7	5 mg/kg/day	2.5 mg/kg b.i.d.
8 to 14	10 mg/kg/day	5 mg/kg b.i.d.
Suggested titration to the maximum dose		
$\geq 15$	$\leq 15$ mg/kg/day	$\leq 7.5$ mg/kg b.i.d.
$\geq 22$	$\leq 20$ mg/kg/day	$\leq 10$ mg/kg b.i.d.
$\geq 29$	$\leq 25$ mg/kg/day (TSC only)	$\leq 12.5$ mg/kg b.i.d.

Abbreviations: b.i.d. = twice a day; DS = Dravet syndrome; LGS = Lennox–Gastaut syndrome; TSC = tuberous sclerosis complex.

Note: Participants with TSC may receive a maximum dose of 25 mg/kg/day; participants with LGS or DS may receive a maximum dose of 20 mg/kg/day.

- If a participant reports any tolerability issues related to GWP42003-P or an AE occurs at any time during the 52-week treatment period, the investigator may temporarily or permanently reduce the participant's dosage, following discussion with the medical monitor. For participants with poor tolerability, the daily dose should be reduced by 10 mg/kg every 7 days (unless smaller, larger, or more rapid dose reductions are clinically indicated per the investigator's opinion).
- At any time, the dose level may be decreased below the target dose (i.e.,  $< 10$  mg/kg/day), based on safety and tolerability, with 2.5 mg/kg/day being the minimum dose. Where possible, the participant should be encouraged to return to the target dose level (10 mg/kg/day); doses may increase in maximum weekly increments of 5 mg/kg/day ( $\leq 2.5$  mg/kg b.i.d.) following consultation with the medical monitor. Investigators should regularly monitor a participant's response to treatment and re-evaluate the need for adjustments to dosage (i.e., increase, maintain, or decrease) at each study visit, if applicable. The rationale for any dosage changes will be documented in the appropriate eCRF.

Following the EOT visit, doses of GWP42003-P will be down-titrated at home (10% of the final dose per day for 10 days) until the end-of-taper visit.

Participants discontinuing the study intervention early should still complete a 10-day taper period (unless a continued dosing is not possible due to an AE or other safety or tolerability considerations); additional information is in [Section 10](#).

Following enrolment, dose adjustments to ASM should not be made without prior consultation with the medical monitor. All adjustments must be captured within the eCRF (refer to [Section 8.2](#)).

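### Protocol 8.1.2: the default dose-reduction step cannot be applied at the starting or target dose without going below the protocol's own minimum dose

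*Protocol*

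**What the plan says.** Everything relevant is in Protocol section 8.1.2 (Dose Escalation and Dose Adjustments).

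- **Starting and target dose.** Treatment begins at 5 mg/kg/day on Day 1. On Day 8, with a 3-day window either way, "the dose will be increased to the target dose level of 10 mg/kg/day". Escalation beyond the target is optional from Day 15.
- **Maximum.** The note to Table 2 reads: "Participants with TSC may receive a maximum dose of 25 mg/kg/day; participants with LGS or DS may receive a maximum dose of 20 mg/kg/day".
- **Default reduction.** For poor tolerability, "the daily dose should be reduced by 10 mg/kg every 7 days". The sentence carries an exception: "unless smaller, larger, or more rapid dose reductions are clinically indicated per the investigator's opinion". The sentence before it says that the investigator may reduce the dose after discussion with the medical monitor, and that this can happen at any point in the 52 weeks. The fixed two-week titration is therefore covered.
- **Minimum.** The following bullet permits doses below the target on safety and tolerability grounds, "with 2.5 mg/kg/day being the minimum dose".

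The reduction sentence does not mention the minimum, and the minimum sentence does not mention the step. SAP section 3.1 repeats that doses may be lowered below target but gives neither a step size nor a minimum, so it does not settle the matter.

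**The concern.** A default reduction step should be usable at the doses participants actually take. Here the step equals the target dose and is twice the starting dose. The minimum-dose bullet plainly expects some children to continue on between 2.5 and 10 mg/kg/day. The default step cannot take a child from the target, or from the starting dose, into that range.

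The target is not a marginal case. It is the level the fixed titration aims for, escalation beyond it is optional, and children who have been reduced are encouraged to return to it. A site dealing with poor tolerability at 10 mg/kg/day therefore has a default and a minimum that cannot both be followed. The participants are infants and toddlers with uncontrolled seizures, so the written rule should be clear at the dose where it is most likely to be consulted.

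**Working it through.** The check is direct arithmetic. The plan gives no derived figure to reproduce; the inputs are stated constants.

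**Inputs (all Protocol 8.1.2):** default step 10 mg/kg off the daily dose, every 7 days; starting dose 5 mg/kg/day; target 10 mg/kg/day; optional levels 15, 20 and (TSC only) 25 mg/kg/day from Table 2; minimum 2.5 mg/kg/day.

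**Formula.** Dose after one step = current dose - 10. A step respects the minimum if current dose - 10 ≥ 2.5, that is, if current dose ≥ 2.5 + 10 = 12.5 mg/kg/day.

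| Current dose (mg/kg/day) | Step as % of dose | After step 1 | After step 2 | After step 3 | Full steps that respect the minimum |
|---|---|---|---|---|---|
| 5 (start) | 200% | not possible (10 exceeds 5) | – | – | 0 |
| 10 (target) | 100% | 0 | – | – | 0 |
| 15 | 66.7% | 5 | not possible | – | 1 |
| 20 | 50% | 10 | 0 | – | 1 |
| 25 (TSC only) | 40% | 15 | 5 | not possible | 2 |

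The largest reduction that the minimum allows is 10 - 2.5 = 7.5 mg/kg/day from the target and 5 - 2.5 = 2.5 mg/kg/day from the starting dose. Both are smaller than the default step.

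**Alternative reading.** If the 10 mg/kg were meant per administration, twice daily, the daily reduction would be 20 mg/kg. That does not fit the words of the sentence, which concern the daily dose, and it widens the conflict: 20 - 20 = 0, and only the 25 mg/kg/day level would survive one step (25 - 20 = 5).

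**The case against.** The best answer is that the step is a recommendation with an exception in the same sentence. The investigator may choose a smaller reduction, reductions follow discussion with the medical monitor, and any dose change needs follow-up within 7 days. Read together, the two bullets could be taken as a general step with discretion, followed by a floor for dosing below target. The step is also workable, at least once, at every Table 2 level above the target.

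Much of this stands. A reader might infer that the protocol sends children at the target dose to zero, or prescribes an impossible dose at the start. It does neither, because the exception lets the investigator avoid both results. What the exception does not do is repair the default. It is triggered by clinical indication, not by the current dose or the minimum, and it permits larger and faster reductions as well as smaller ones. At 5 and 10 mg/kg/day the default can be reconciled with the minimum only by leaving the default.

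Three further readings are tempting and are not supported.

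- **Conflict with the taper.** The end-of-treatment rule is that "doses of GWP42003-P will be down-titrated at home (10% of the final dose per day for 10 days". It governs stopping, whether at the end of treatment or early, and not dose reduction in a child who continues. Section 8.1.2 also waives it on early discontinuation where safety or tolerability prevents further dosing.
- **Corrupted adverse-event data.** The case report form records the action actually taken with the study drug (Protocol 12.5, item F), and SAP section 6.1.9.1 derives its categories from that entry. Nothing in the documents shows that sites acted or coded differently because of this wording.
- **Every child reaches the target.** Protocol section 4.1 exempts those who cannot tolerate it.

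**Conclusion.** The point holds as an internal contradiction in a stated dosing rule. With no lower limit on when it applies, one default step breaches the 2.5 mg/kg/day minimum at any current dose below 12.5 mg/kg/day, including the starting and target doses. At 15 and 20 mg/kg/day the second weekly step breaches it, and at 25 mg/kg/day the third does.

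This rests on two assumptions: that the step applies to the daily dose, as written, and that the minimum applies to every child who continues treatment. It does not depend on the taper rule or on any effect on the analysis, and it does not show that any child received a dose below the minimum.

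The wording should be corrected, but the practical reach is limited. SAP sections 1 and 9.6 record the decision of 28 January 2025 to end the study, so the correction matters for any dosing that remained and for any later protocol that reuses this text.

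**What to change.** The sponsor's clinical team should reconcile the reduction-step sentence with the minimum-dose sentence in Protocol 8.1.2, so that the default, applied once or repeatedly, cannot give a dose below the stated minimum. The text should make clear how the default operates at the starting dose, at the target dose and on repeated weekly steps. Which figure or rule changes is a clinical decision, and none is proposed here.

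The cost is a wording amendment or a clarification letter, with no added visits, procedures or data collection and no change to the SAP. If no participant remains on treatment, it is enough to correct the text before it is used again.
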